### **Subgroup analyses**

Rather than stratifying the analysis by subgroups, the intention is to extend the primary outcome analysis by including the main effect(s) and interaction terms for the variables listed below. These interactions will be exploratory and, to account for multiple testing, a false discovery rate adjustment will be made to p-values using the *p.adjust* function in R. Tests for variables with multiple categories will be reported at each level with 95% confidence intervals (CIs) with the inference based on an omnibus test across all levels.

- Ethnicity will be derived from self-reported pupil and staff survey data. Response options include broad ethnic classifications: Asian, Black, Mixed, White, Other, and Prefer not to say. These categories will be dummy coded with White as the reference category. They will then be integrated as interaction terms with group allocation, with pupil and staff categories incorporated into outcome models specific to each group.
- Pupil FSM eligibility will be obtained from local school administrative data in two waves: summer 2024 and summer 2025. This will be dummy coded (yes/no) and will be included as an interaction term with group allocation in pupil-specific outcome models.
- Pupil SEND/EHCP status will be obtained from local school administrative data. SEND/EHCP status will be a binary category, and pupils receiving any SEND support or who have an EHCP will be counted within the SEND/EHCP group. This will be dummy

coded (yes/no) and will be included as an interaction term with group allocation in pupil-specific outcome models.

We will also include a cross-level interaction between group allocation and scores on the staff-reported empathy and control sub-scales of the ARTIC 35 (Baker et al., 2021)

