### **Imbalance at baseline**

Table 1 provides baseline descriptive statistics for intervention and control groups, as well as the p-values for the t-tests for continuous data and chi-square tests (post-hoc test p-values in brackets) for count data. Members of the research team who are unblinded to intervention group allocation have access to the data in this table.

The school-level percentage of pupils eligible for free school meals and percentage of pupils with SEND or EHCP status was acquired through public data and averaged for intervention and control schools.

The pupil and staff descriptive statistics are from the baseline self-report pupil and staff surveys. Data from participants who had complete primary outcome data available (SDQ externalising for pupils and ARTIC-35 for staff) are included in the table. Please note that data on year group (year 8 or year 9) is currently only available for cohort 2 schools. Year group data for cohort 1 pupils is shown as missing and will be obtained from the school administrative data in July 2024.

In terms of imbalance at baseline, there are more females and less males in the intervention schools compared to control schools. This can be explained by a higher proportion of boys' schools present in the control group. Furthermore, intervention schools had a higher mean score on three out of the five ARTIC-35 sub-scales (Response to Problem Behaviour, On the Job Behaviour (Empathy and Control) and Reactions to Work) compared to control schools. This indicates that staff in the intervention schools have greater alignment with trauma-informed practice beliefs in those areas compared to the control schools. This may be partially explained by the differences in the staff response rate between intervention and control

schools (intervention: 35.1%, n = 29 schools; control: 28.3%, n = 28 schools). Please note that the response rates do not include schools who have not yet provided total school staff numbers; two are missing in the intervention arm, and three in the control arm.

Table 1. Baseline descriptive statistics of schools, pupils, and staff at baseline, split by intervention and control group.

	Intervention group (n = 31 schools)	Control group (n = 31 schools)	p
School-level	Mean (SD)	Mean (SD)	
Percentage of pupils with FSM eligibility	28.6% (10.6%)	28.2% (13.5%)	0.89
Percentage of pupils with SEND/EHCP status	15.6% (4.5%)	16.5% (4.6%)	0.41

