### **Missing data**

We will explore the amount of missingness in the data, such as the percentage of missing values per variable. We will evaluate the extent to which data are systematically missing by investigating which baseline variables are associated with missingness for the primary outcome of externalising symptoms at the end of programme time point. Multi-level logistic regression will be conducted to identify variables that predict missingness (0 = not missing, 1 = missing).

Intervention schools that have withdrawn post-randomisation will still be asked to participate in the follow-up data collection periods, to minimize missing data and the need for imputation.

We will have two approaches to addressing missing data and we will compare the results between approaches:

- 1) Multiple imputation will be conducted for any baseline and follow up data. Data will be imputed with data in wide format without clustering for time, as time will be included as a dummy coded variable in the analysis. The package *mice* will be used to impute missing values (van Buuren & Groothuis-Oudshoorn, 2011). The quickpred

function within mice will be used with a minimum correlation of 0.25 to build the predictor matrix for imputation. School will also be specified as a predictor in the predictor matrix. At least 25 imputations will be specified; the number of imputations will match the percentage of missing data. Analyses will be run with these datasets with the pooled estimates derived.

- 2) Participants with at least one post-randomisation datapoint (i.e. mid-programme or end of programme) will be included and analyses will be run with maximum likelihood estimation.

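### The imputation model has no arm-by-moderator terms, so the multiply imputed pupil-level subgroup interactions are biased toward zero, by up to about a quarter at 25% attrition

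*SAP*

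**What the plan says.** The SAP's Missing data section plans two approaches and a comparison between them. In approach 1, wide-format data are imputed with mice, and the quickpred "function within mice will be used with a minimum correlation of 0.25 to build the predictor matrix for imputation". One variable is added whatever its correlation: "School will also be specified as a predictor in the predictor matrix". Neither product terms nor imputation by arm is mentioned, and neither arm nor any moderator is forced in. The section continues: "Analyses will be run with these datasets with the pooled estimates derived". It makes no exception for subgroup analyses. Approach 2 is maximum likelihood without imputation. The SAP does not say which approach takes precedence.

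Under Subgroup analyses, "the intention is to extend the primary outcome analysis by including the main effect(s) and interaction terms for the variables listed below". FSM eligibility and SEND/EHCP status each "will be included as an interaction term with group allocation in" the pupil outcome models, and ethnicity is treated in the same way. One moderator comes from staff: "We will also include a cross-level interaction between group allocation and scores on the staff-reported empathy and control sub-scales of the ARTIC 35".

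**The concern.** An imputation model should contain at least the structure that the analysis model will test. Here the analysis asks whether the programme effect differs by FSM, SEND/EHCP or ethnicity, while the imputation model has no term through which it could differ. Imputed outcomes then carry little or none of any true difference. Mixing them with observed outcomes pulls the estimated interaction toward zero.

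Two things are at stake. The SAP concedes that some of these tests will be underpowered, and a one-directional bias adds to the risk of missing a real difference. In addition, the comparison of the two approaches is meant to inform the reader about missing data. For these interactions it would instead reflect a defect in the imputation model.

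**Working it through.** **Inputs from the SAP.** Pupil attrition 25% (Sample size calculations overview); 62 schools of about 220 pupils, ICC 0.041, cluster-size CV 0.366 (same section); pupil counts by ethnicity and arm, and school-level percentages such as "Percentage of pupils with FSM eligibility" of 28.6% and 28.2% (Table 1); SEND/EHCP 15.6% and 16.5% (Table 1).

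**Assumptions not in the SAP.** Correlation between waves about 0.6 to 0.7; moderator main effect 0.3 SD; true interaction 0.2 SD, equal at both follow-ups; data missing completely at random; missing share varied from 15% to 40%.

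**The plan's own figure.** The SAP gives no figure for imputation bias. The nearest one that can be reproduced is the sample size at randomisation. For a difference of 0.51 and SD 2.96, the unclustered n is 528.79 per arm. The design effect is 1 + 218.73 × 0.041 = 9.968. Dividing 528.79 × 9.968 by 219.73 gives 23.99 schools, and allowing for unequal cluster sizes gives 24.27 schools and 5333.03 pupils per arm. The SAP states 24.3 and 5333.02, so the cluster inputs are read correctly.

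**Would the screen keep the moderators?** For a yes/no variable with prevalence p, the difference in SD units that gives correlation r is d = √[r²/(1−r²) ÷ p(1−p)]. At r = 0.25, r²/(1−r²) = 0.0667.
- FSM, p = 0.284: √(0.0667/0.2033) = 0.57 SD
- SEND/EHCP, p = 0.16: √(0.0667/0.1344) = 0.70 SD
- Asian 0.61 SD, Black 1.08 SD, Mixed 1.25 SD, Other 1.36 SD

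A difference of 0.3 SD gives r of only 0.13 (FSM) or 0.11 (SEND/EHCP). Screening out is therefore plausible, but the result below does not depend on it.

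**Mechanism.** Let f be the share of pupils with imputed outcomes.
- If they miss both follow-ups, their imputed interaction is about zero, so the expected ratio to the true interaction is 1 − f. At f = 0.25 this is 0.75.
- If they miss only the end point, the observed mid-programme score carries part of the interaction, and the ratio at the end point is (1 − f) + f·b, where b is the coefficient of the mid score given baseline. With equal correlations ρ between waves, b = ρ/(1 + ρ). For ρ = 0.6, b = 0.375 and the ratio is 0.75 + 0.25 × 0.375 = 0.84. For ρ = 0.7 it is 0.85.

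**Simulation of the SAP's rule.** 62 schools of 220 pupils, moderator prevalence 0.28, imputation from baseline, school dummies and the other wave, 5 imputations, 25 replicates. Entries are the multiply imputed arm-by-moderator estimate divided by the full-data estimate.

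| Missing pattern | Two-wave average | End point |
|---|---|---|
| 15% miss both | 0.86 | 0.86 |
| 25% miss both | 0.76 | 0.76 |
| 40% miss both | 0.60 | 0.59 |
| 12.5% both, 12.5% end only | 0.82 | 0.77 |
| 25% miss end only | 0.93 | 0.85 |

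- Moderator main effect added, no product: 0.76 (average) and 0.75 (end point) at 25% missing both, so no gain.
- Moderator and product with arm added: 0.98 to 1.03 in every pattern.
- Analysis of the observed data in the manner of maximum likelihood: 0.98 to 1.02.
- School-level moderator by arm, school as dummies: 0.98 to 1.04.
- School entered as a numeric code, 25% missing both: the main effect of arm at the end point also falls, to 0.74. Arm would not be rescued by the screen, since an effect of 0.17 SD gives r = 0.085.

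A second simulation at 25% missing (wave correlation 0.6 to 0.7, 20 replicates) gave 0.74 to 0.75 when both waves were missing. With only the end point missing it gave 0.86 to 0.88 at the end point and 0.93 to 0.94 on the average. With each wave missing independently it gave about 0.84.

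**The case against.** The best defence is that little hangs on this. The SAP declares the subgroup interactions exploratory, adjusts them for false discovery rate and warns against reading them individually. An unattenuated maximum likelihood estimate will be available beside the imputed one. This stands as a reason to rate the point as modest. It does not remove the error: the exploratory label guards against chance findings, not against a foreseeable bias in one direction.

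Several stronger readings are tempting, and the SAP does not support them:
- A reader might infer that every subgroup interaction is biased. The staff empathy-and-control interaction varies between schools, and school is in the imputation model. If school enters as dummies, that interaction is preserved.
- A reader might take the attenuation to equal the missing share. That holds only when pupils miss both follow-ups. Wide-format imputation lets an observed mid-programme score carry part of the interaction.
- A reader might blame the 0.25 screen. The SAP gives no moderator-outcome correlations, its FSM and SEND/EHCP percentages are school-level public figures, and quickpred also keeps variables that correlate with missingness. Dropping the moderators is thus an inference, and keeping their main effects would not help.
- A reader might compound pupil and school attrition to about 36% (1 − 0.75 × 0.85). Both are planning allowances, and the SAP will still approach withdrawn intervention schools for follow-up data.
- A reader might conclude that the primary effect is biased as well. That would follow only if school were entered as a numeric code, and the SAP does not state the coding.

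**Conclusion.** Wrong as written, with modest severity. Under approach 1, the stated imputation rule biases the group-by-ethnicity, group-by-FSM and group-by-SEND/EHCP interactions toward zero, with or without the moderators' main effects in the imputation model. At 25% missing, attenuation is up to about 25% if pupils miss both follow-ups. If they miss only the end point, it is about 12 to 15% there and about 6 to 7% on the two-wave average. These sizes rest on the assumed wave correlations of about 0.6 to 0.7, data missing completely at random and an interaction of similar size at both waves. The direction of the bias does not depend on the exact values. The maximum likelihood approach is not affected, so on these interactions the two approaches would differ for a reason built into the imputation model.

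**What to change.** Amend approach 1 in the SAP's Missing data section as follows:
- Run mice separately within each arm. Alternatively, force arm, the moderators and their products with arm into the predictor matrix.
- Force in FSM, SEND/EHCP, ethnicity, gender and year group whatever their correlations.
- State that school enters as a categorical factor and not as a numeric code. Cohort and LA/CA are fixed within school and then need not be added.
- Use the 0.25 screen only to add further auxiliary variables.

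In simulation, adding the moderator and its product restored the interaction to 0.98 to 1.03 of the full-data value. Imputing within arm with the moderator forced in gave 95 to 102% of the true value. The cost is a sentence or two in the SAP, a few lines of code and slightly larger imputation models.

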## Compliance

Compliance with MGDAS will be assessed with two methods. Information gathered from these methods will be compared against intended delivery using the MGDAS intervention description. Outlined below is the type of data collected and the proposed analysis.

1. Activity data will be collected by the MGDAS programme team to examine, for example, number and types of sessions delivered and number and types of school staff attending each session. The average percentage of eligible staff attendance across the three types of sessions (whole school staff, pastoral and inclusion leads, and senior leadership team) will be used as the indicator of compliance.

Complier average causal effect (CACE) analysis will be used to estimate the intervention effect for a hypothetical scenario where everyone was adherent. The average percentage of eligible staff attendance across training sessions for each intervention school will be used as the compliance measure. The threshold for compliance will be specified as 80%. If there are too few schools reaching 80% compliance or above, we will use the upper quartile of the average percentage as the threshold. We will aim to conduct CACE analysis through bespoke programming due to the outcome data being at the pupil level but the compliance metric being at the cluster (school) level. This will account for the first stage regression at the cluster level and the second stage regression at the individual outcome level with adjustment for cluster. If bespoke programming is not possible, the `caceCRTBoot` function in the *eefAnalytics* package in R will be used to conduct the CACE analysis clustered by school. CACE analysis will be conducted irrespective of whether the intervention effect is significant or non-significant. If the effect is non-significant, this sensitivity analysis will be useful to determine whether a non-significant main intervention effect was due to the intervention itself or a lack of adherence.

2. The support description survey completed by the single point of contact at each school, to examine changes to policies and practices implemented by schools after the MGDAS programme. We will create a composite score of school-level compliance with assigned condition based on the number and type of changes implemented and the stage of implementation. It should be noted that we are not attempting to restrict implementation of changes to policy and practice for schools allocated to business as usual only.

A descriptive analysis will be undertaken to examine whether there are differences in the levels of changes to policies and practices according to assigned condition (i.e., MGDAS and business as usual, business as usual only).

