The section with actual sample size and MDES at randomisation were updated following randomisation in February 2024. The average cluster size for pupils who completed the

primary outcome (SDQ externalising symptoms items) was 219.73, rounded to 220 pupils in the table. Furthermore, intracluster correlation was calculated as 0.041 and coefficient of variation was 0.366. With these parameters, we are powered to detect MDES of 0.17. Please see the following STATA code, which estimates the number of schools as 24.3 and the number of pupils per arm as 5333.02, inflated to 29 schools and 6372 pupils per arm based on 15% school attrition: `power twomeans 5.21 4.7, sd(2.96) rho(0.041) m1(219.73) m2(219.73) power(0.8) cvcluster(0.366) nfrac display "schools per arm = " ceil(r(K1)/.85) display "pupils per arm = " round(ceil(r(K1)/.85)*219.73).`

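### The upper-quartile CACE fallback fixes the complier share at about a quarter whatever attendance was, and CACE cannot show why a result is non-significant

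*SAP*

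**What the plan says.** All of this is in the SAP, section Compliance.

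- **Aim:** "Complier average causal effect (CACE) analysis will be used to estimate the intervention effect for a hypothetical scenario where everyone was adherent".
- **Measure:** "The average percentage of eligible staff attendance across training sessions for each intervention school will be used as the compliance measure". A school complies at 80% or more.
- **Fallback:** "If there are too few schools reaching 80% compliance or above, we will use the upper quartile of the average percentage as the threshold". The SAP gives no number for too few and no minimum attendance below which the fallback would not apply.
- **Estimator:** "This will account for the first stage regression at the cluster level and the second stage regression at the individual outcome level". Clustering by school is allowed for in the second stage. A packaged routine is named in case bespoke programming is not possible.
- **Use:** the analysis is run whether or not the ITT result is significant. If it is not, the CACE is described as "useful to determine whether a non-significant main intervention effect was due to the intervention itself or a lack of adherence".

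No other section of the SAP qualifies the fallback or the stated use.

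**The concern.** A two-stage CACE with a yes/no compliance variable divides the ITT effect by the share of intervention schools classed as compliers. It assumes that the other schools gained nothing from the training.

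When the cut is a quantile of the observed attendance, that share is set by the choice of quantile. The first stage then says nothing about how well schools attended, which is the information the analysis exists to use. A school just below the cut may have almost the same attendance as one just above it, yet the whole ITT effect is credited to the schools above.

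Two things are at stake. A figure labelled as the effect under full adherence could be published although its size comes from the choice of cut-off. And the SAP gives advance licence to read a null result as an adherence problem on evidence that cannot show it.

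**Working it through.** **Inputs from the SAP.** 31 schools per arm (Sample size calculations overview; Table 1). MDES at randomisation 0.17, ICC 0.041, mean cluster size 219.73, CV of cluster size 0.366, SD 2.96, means 5.21 and 4.70, two-sided alpha 0.05, power 0.80.

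**1. The plan's own figure.** The SAP states no CACE figure, so the MDES calculation is the benchmark for the ITT effect.
- Unclustered n per arm = 2 × (2.96 × (1.960 + 0.842) / 0.51)² = 528.8.
- Design effect = 1 + 218.73 × 0.041 = 9.97.
- For unequal clusters, divide by 1 − CV² × L × (1 − L), with L = 219.73 × 0.041 / (219.73 × 0.041 + 0.959) = 0.904. This gives 10.09.
- Schools per arm = 528.8 × 10.09 / 219.73 = 24.3. Then 24.3 / 0.85 rounds up to 29 schools, and 29 × 219.73 = 6372 pupils. Both agree with the SAP.

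**2. Multiplier under the fallback.** CACE = ITT / (complier share in intervention arm − share in control arm). The control share is taken as 0, because compliance is defined for intervention schools only.
- Six of seven common quantile definitions put 8 of 31 schools at or above the cut: 8/31 = 25.8%, multiplier 31/8 = 3.9. The seventh gives 9/31, multiplier 3.4.
- With pupil weighting (school sizes simulated with CV 0.366), the share lies between about 20% and 32%, multiplier 4.9 to 3.2.
- With attendance data from only 29 or 26 schools, it is 29/8 = 3.6 or 26/7 = 3.7.
- ITT effects of 0.05, 0.10 and 0.17 SD become 0.19, 0.39 and 0.66 SD.

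**3. Does it respond to adherence?** The SAP gives no attendance figure. Three simulated sets of 31 schools (assumed distributions), with the ITT effect held at 0.10 SD:

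| Mean attendance | Upper-quartile cut | Fallback CACE | Schools at 80% | Multiplier keeping 80% | ITT / mean attendance |
|---|---|---|---|---|---|
| 32% | 38% | 0.39 | 0 | not estimable | 0.31 |
| 56% | 68% | 0.39 | 1 | 31 | 0.18 |
| 73% | 77% | 0.39 | 6 | 5.2 | 0.14 |

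The fallback column is constant. The last column is the effect at 100% attendance if the effect is proportional to attendance.

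**4. Against the 80% rule.** With 3 of 31 schools at 80%, the 80% rule multiplies by 31/3 = 10.3 and the fallback by 3.9. With 8 or more schools at 80%, a cut that selects 8 adds no school.

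**5. Test statistic.** If p is the complier share, CACE = ITT/p and its standard error is approximately SE(ITT)/p, so z is unchanged. Under the fallback p is fixed by construction. Elsewhere, the uncertainty in p contributes terms that vanish as ITT approaches 0, which is the case at issue. Illustration: the SE implied by the MDES is 0.17 / (1.960 + 0.842) = 0.061.
- ITT 0.10: z = 1.65, 95% CI −0.02 to 0.22.
- Fallback CACE 0.39: SE = 0.0607 × 3.875 = 0.235, z = 1.65, 95% CI −0.07 to 0.85.

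The test result is the same and the point estimate is larger.

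**The case against.** The strongest reply has four parts.

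- **It is a conditional branch of a sensitivity analysis.** The ITT mixed model carries the primary inference and is untouched. This stands, and it limits the severity.
- **The fallback is the gentler rule where it loosens anything.** This also stands (step 4). A reader might infer that the fallback causes the inflation and that keeping 80% would cure it. The arithmetic does not support that. Assuming no effect below the cut is a feature of both rules.
- **A null ITT stays null.** A reader might infer that the CACE could turn a non-significant result into a significant one. It cannot, because the interval widens by the same factor. What remains is the risk of over-reading a large, imprecise estimate, which the SAP's sentence on interpretation invites. Attendance will be described alongside, which helps but does not correct that sentence.
- **Continuous attendance brings its own assumption.** It does: linearity, and possibly extrapolation. But its first stage is mean attendance, so unlike the fallback it moves with adherence.

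**Conclusion.** The point holds and should be fixed, as a matter for the sensitivity analysis only.

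Under the fallback the complier share is about 8/31 and the multiplier about 3.9, or roughly 3 to 5 once ties, weighting and covariates are allowed for. This rests on 31 intervention schools, no training in control schools and a two-stage ratio estimator. The SAP does not describe the internals of the packaged alternative, so the figure is not claimed for it. The result carries no information about actual attendance and does not "estimate the intervention effect for a hypothetical scenario where everyone was adherent".

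How far it overstates a full-adherence effect cannot be read from the SAP. If the effect is proportional to attendance and mean attendance is 50% to 70% (both assumptions), the overstatement is 3.875 × 0.5 = 1.9 to 3.875 × 0.7 = 2.7 fold. On the same assumption it would vanish at a mean of 25.8% and reverse below that. The range is illustrative, and a reader should not take it as a property of this trial.

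The statement that CACE can settle the cause of a non-significant result is wrong under any threshold, so that part stands even if the fallback is never used.

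**What to change.** 1. Remove the upper-quartile fallback, and with it the undefined trigger.
2. Make the main CACE an instrumental-variable analysis of continuous school attendance (0 in control schools), instrumented by allocation and with clustering by school. Report it per 10 percentage points. Label any value at 100% as an extrapolation if no school attended at that level.
3. Keep the 80% version only as a secondary display. Give with it the number and share of schools reaching 80%, the implied multiplier, and a statement that it assumes no effect below 80%. If no school reaches 80%, say that it cannot be estimated.
4. Delete the sentence claiming that CACE determines why a result is non-significant. The continuous version rescales estimate and standard error together in the same way, so it does not rescue that claim.

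The cost is SAP wording and a modest change to code not yet run, since the attendance percentages are already to be collected. The downside is that the continuous analysis assumes a linear dose-response, which should be stated beside the result.

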## Sample size calculations overview

		Protocol	Randomisation
Minimum Detectable Effect Size (MDES)		Standardised mean difference = 0.15	Standardised mean difference = 0.17
Pre-test/ post-test correlations	level 1 (participant)	-	-
	level 2 (cluster)	-	-
Intracluster correlations (ICCs)	level 1 (participant)	0.03	0.041
	level 3 (cluster)	-	-
Alpha		0.05	0.05
Power		0.8	0.8
One-sided or two-sided?		Two-sided	Two-sided
Average cluster size		186 pupils 159 staff	220 pupils 26 staff
Number of clusters	intervention	29	31
	control	29	31
	total	58	62

		Protocol	Randomisation
Number of participants	intervention	4650 pupils 3975 staff	6429 pupils 724 staff
	control	4650 pupils 3975 staff	7194 pupils 896 staff
	total	9300 pupils 7950 staff	13623 pupils 1620 staff

The cluster sample size was determined a priori using a minimum detectable effect size (MDES) of 0.15 (standardised mean difference). The protocol presented different scenarios for sample size calculations based on a MDES between 0.10 and 0.20 (see Table 4 in the trial protocol). Presented in the table above is the sample size calculation for MDES of 0.15, which is in line with a projected school recruitment of 55 schools inflated to account for 15% attrition (58 in total). The estimate for the mean and SD of externalising difficulties in the control arm was based on the combined female and male scores from Elia et al. (2020). The intraclass correlation coefficient was assumed as 0.03. There is a lack of evidence on which to base assumptions for the pre-post correlation of externalising difficulties, so the sample size calculations were not adjusted to account for this. STATA was used for the power calculation using the following code: (MDE 0.15) power twomeans 5.21 4.76, sd(2.96) rho(0.03) m1(186) m2(186) power(0.8) cvcluster(0.5) cluster = 25 schools and 4,650 pupils per arm (increased to 29 schools per arm based on 15% school attrition).

The primary population of interest is pupils; estimates are also presented for staff. The pupil and staff sample sizes were determined from figures from three initial Local Authorities (LAs; Kent, Slough and Wiltshire). From this, 186 pupils per school were assumed after accounting for 35% study refusal and 25% attrition, resulting in an estimated sample size of 9300 pupils in total. 159 staff per schools were assumed after accounting for 35% study refusal and 25% attrition, resulting in 7950 staff in total.

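### A non-significant CACE after a non-significant ITT effect cannot by itself separate an ineffective programme from poor adherence, although the SAP gives it that use

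*SAP*

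**What the plan says.** The Compliance section of the SAP measures adherence at school level, as mean attendance of eligible staff over the training sessions, for intervention schools only. A school counts as compliant at 80%. If too few schools reach that level, the cut-off becomes the upper quartile of attendance. The CACE is to come from a two-stage model, with the first stage at school level and the second at pupil level.

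The section then states: "CACE analysis will be conducted irrespective of whether the intervention effect is significant or non-significant". For the non-significant case it says the analysis will be "useful to determine whether a non-significant main intervention effect was due to the intervention itself or a lack of adherence". It attaches no decision rule, no statement of precision and no assumptions, and no other part of the SAP qualifies the sentence. The same section plans to compare delivered with intended sessions, and to describe changes in policy and practice by arm. The task of explaining a null result is given to the CACE alone.

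**The concern.** A null primary result has at least two competing explanations: the programme does not work, or it was not taken up. The SAP says in advance that the CACE helps to decide between them. If the CACE rescales the ITT estimate and its standard error by the same factor, it adds no independent evidence on that question, and its p-value is close to the one already in hand.

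A reader who follows the SAP's sentence could then err in two ways. A non-significant CACE could be read as showing that the programme itself is ineffective, when the interval is simply wide. A CACE point estimate larger than the ITT estimate could be read as showing that the programme works when delivered, when the ratio comes from dividing by a fraction. What is at stake is how a null efficacy trial is interpreted. The primary estimate does not change.

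**Working it through.** **Inputs.** From the SAP's Sample size calculations overview: alpha ("Alpha 0.05 0.05"), two-sided testing ("One-sided or two-sided? Two-sided Two-sided"), the means and SD in the code ("power twomeans 5.21 4.7, sd(2.96"), and the clustering parameters ("rho(0.041) m1(219.73) m2(219.73) power(0.8) cvcluster(0.366"). The same table and Table 1 give 31 schools per arm. The SAP has no attendance data, so the compliant share *c* and the ITT effect below are assumptions.

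**Step 1: reproduce the SAP's figure.**
- Unclustered n per arm = 2 × (2.96 × (1.960 + 0.842) / 0.51)² = 528.8.
- Design effect = 1 + (219.73 - 1) × 0.041 = 9.968.
- L = 219.73 × 0.041 / 9.968 = 0.904. Relative efficiency for unequal clusters = 1 - 0.366² × L(1 - L) = 0.988.
- Schools per arm = 528.8 × 9.968 / (0.988 × 219.73) = 24.27, or 5333 pupils. Dividing by 0.85 and rounding up gives 29 schools and 6372 pupils.

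This agrees with the SAP (24.3 schools and 5333.02 pupils, "inflated to 29 schools and 6372 pupils per arm based on 15% school attrition"), for which it says "we are powered to detect MDES of 0.17" (0.51 / 2.96 = 0.172).

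**Step 2: standard error of the ITT effect by the same method, in SD units, 31 schools per arm.** SE = √(2 × 9.968 / (0.988 × 219.73 × 31)) = 0.054. This takes no credit for the baseline covariate, as the SAP's own calculation does not.

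**Step 3: CACE.** With no control school coded as compliant, CACE = ITT / *c* and, to first order, SE(CACE) = SE(ITT) / *c*. Hence z(CACE) = z(ITT) for any *c*. With an assumed ITT benefit of 0.08 SD (benefit, a lower score, written as positive), z = 0.08 / 0.0544 = 1.47 and p is about 0.14:

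| *c* | CACE | SE | 95% CI | z |
|---|---|---|---|---|
| 1.0 (ITT) | 0.08 | 0.054 | -0.03 to 0.19 | 1.47 |
| 0.8 | 0.10 | 0.068 | -0.03 to 0.23 | 1.47 |
| 0.4 | 0.20 | 0.136 | -0.07 to 0.47 | 1.47 |

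**Step 4: check by simulation.** School-level two-stage least squares was run on 10,000 simulated trials per scenario, with 31 schools per arm of equal size and ICC 0.041. Attendance was assumed to follow Beta(6,4), mean 60%. Fewer than eight schools at 80% was taken as too few, so the upper-quartile fallback applied and about 8 of 31 schools (25.8%) counted as compliant. Among trials with a non-significant ITT effect, the CACE was significant in:
- 0.01% when the programme had no effect;
- 0.07% when the effect was proportional to attendance (0.17 SD at full attendance);
- 0.65% when only top-quartile schools benefited, by 0.17 SD.

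Three different truths give almost the same outcome. Where the two tests disagreed, it was mostly because the CACE test was the more conservative (1.8% against 5.1% rejection with no effect).

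The point estimate does not separate mechanisms either. A uniform 0.05 SD effect unrelated to attendance gave a mean CACE of 0.19. A 0.17 SD benefit confined to top-quartile schools gave 0.17.

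**Step 5: when the interval does say something.** Around an ITT estimate of zero, the CACE half-width is 1.96 × 0.0544 / *c* = 0.107 / *c*. That is 0.133 at *c* = 0.8 and 0.267 at *c* = 0.4. It falls below 0.17 when *c* exceeds 0.63 (20 of 31 schools) and below 0.20 when *c* exceeds 0.53 (17 of 31).

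**The case against.** The strongest reply is that the SAP claims only usefulness, in one sentence about a sensitivity analysis. The ITT mixed model remains the basis of the main report, and attendance monitoring and process data will also be available. All of that stands. It makes this a matter of interpretation and limits its weight, but it does not make the sentence correct.

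A second reply is that the CACE can bear on efficacy. This also stands in part. Step 5 shows that with high compliance the interval can exclude an effect of 0.17 or 0.20 in compliant schools. A reader might infer that no CACE result could ever help, and the figures do not support that. The ITT interval and the compliant share already imply the same conclusion, however: at *c* = 0.8, a complier effect of 0.17 corresponds to an ITT effect of 0.136, outside ±0.107. The information lies in the interval, not in non-significance.

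A reader might also infer that lower adherence always inflates the CACE. That holds only for a fixed ITT estimate, as in the Step 3 table. Under the exclusion restriction, lower adherence shrinks the ITT effect and leaves the expected CACE unchanged. In the simulation, CACEs above the true effect at full attendance arose where partly trained schools that did benefit were coded as untreated, which breaks that restriction.

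**Conclusion.** The point holds in a limited form. A non-significant CACE following a non-significant ITT effect does not by itself distinguish an ineffective programme from poor adherence. The algebra applies under the 80% rule as well as the fallback, so changing the threshold would not cure it. The simulation covered the fallback only.

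The result rests on allocation being the sole instrument, no control school being coded as compliant, and the first-order standard error. The 0.08 SD effect and the compliant shares are illustrative. Baseline adjustment would shrink the SE, and loss of schools would widen it, but z would still not depend on *c*.

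It would go too far to say that a null result will be misattributed. The SAP sets no decision rule, so misattribution is a risk if its sentence is applied. This is a wording correction worth making before results are known. It leaves the primary analysis untouched.

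**What to change.** Delete the sentence that gives the CACE the task of explaining a non-significant effect. In its place:

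- Report the CACE with its 95% CI beside the ITT effect, described as the estimated effect in compliant schools. State its assumptions, including the exclusion restriction: allocation has no effect on pupils in schools below the attendance cut-off.
- Conclude that there is no worthwhile effect even in compliant schools only if the benefit-side confidence limit excludes an effect size fixed in advance. A lower externalising score is better, so for intervention minus control this is the lower limit, which must lie above minus the chosen size. The SAP's own candidates are 0.17 (detectable at randomisation) and 0.20 (the funder's requirement, under Interim analyses and stopping rules). The SAP presents both as detectable effects rather than as worthwhile ones, so the team must choose and justify the margin.
- Otherwise state that the trial cannot separate lack of efficacy from lack of adherence.
- Keep the planned comparison of attendance with intended delivery as the descriptive evidence on adherence.

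The cost is a change of SAP wording, with no new data or model. The downside is a more modest claim from the CACE analysis.
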